4. Special Populations

This research does not involve any special populations.

5. RESEARCH ABSTRACT

Please provide a brief description in LAY language (understandable to an 8th grade student) of the aims of this project.

Aging is the primary risk factor for Alzheimer's disease (AD) which is the most common form of dementia and among the fastest growing causes of morbidity and mortality in the United States. The risk factors for AD emerge during midlife and are similar to cardiovascular and cerebrovascular diseases. The impact of midlife vascular changes on the brain are worsened by poor lifestyle habits, including eating a diet that contains a lot of added sugars (e.g., ultra-processed foods containing high amounts of fructose). One effect of eating a high sugar diet is an elevation in blood triglycerides (TGs), which impairs blood vessel function by causing inflammation; however, it is not known whether eating a lot of added sugars affects the blood vessels in the brain. The purpose of this project is to determine if there is a link between added sugar intake and brain health in midlife adults. Our hypothesis is that eating excess added sugar impairs the structure and function of an area of the brain called the hippocampus by increasing plasma TGs and systemic inflammation. To test this, we will have people eat a high and low sugar diet for 10 days each (in a random order) and test how each diet affects their blood vessel function, the structure of their hippocampus, and their memory performance. We expect to show that eating a diet that contains a lot of added sugars worsens brain health compared to a diet that contains few added sugars. The data generated from this project will help us better understand risk factors for dementia and will be used to support a future grant proposal to the National Institutes of Health aimed at lowering added sugar intake in mid-life adults and individuals with mild cognitive impairment.

6. PROCEDURES Describe all procedures involving human subjects for this protocol. Include copies of all surveys and research measures.

6.1 Study Design

We will conduct a single-blind, randomized-crossover, controlled feeding study (see *Protocol Schema on next page*). We will provide subjects with 10-days each of a research diet containing low sugar (LS; 5% of energy) vs. high sugar (HS; 25% of energy) in a random order, separated by a 2-week washout. Primary and secondary outcomes will be measured at baseline and at the end of each 10-day intervention.

6.2 Schedule of Activities

[figure not shown]
Table 6.1

		Screening		Baseline		Diet #1					Diet #2					
		Day of Diet	NA	NA	NA	NA	0	7	9	10	10	0	7	9	10	10
	Visit Number	1.1	1.2	2.1	2.2	3.1	NA	NA	3.2	3.3	4.1	NA	NA	4.2	4.3	
	Duration (hours)	1.5	1.0	1.5	2	0.5	---	---	1.5	2	0.5	---	---	1.5	2	
Eligibility Criteria	Informed Consent	•														
	Demographics	•														
	Medical History	•														
	Menstrual History	•														
	PHQ-9 (depression)	•														
	MRI Safety Form	•		•						•					•	
	COVID-19 Form	•	•	•	•	•				•		•			•	
	MAQ	•														
	3-day diet record	®	—													
	Height		•													
	Body Mass		•				measured at home daily					measured at home daily				
	Body Composition		•								•					•
	Vital Signs		•	•	•						•				•	
	Clinical Labs		•								•				•	
Control Measures	Family History	•														
	PROMIS Measures	•														
	Sleep Quality	•														
	Food Preferences	•														
	APOE genotyping		•													
	Blood Biomarkers		•							•					•	
	Urine collection		•							•					•	
	IPAQ			•						•					•	
	Sleep Questionnaire				•					•					•	
	Sleep Quality				®	—	®			—	®				—	
Outcome	Appetite Survey			•			measured at home daily					measured at home daily				
	24-hr urine collection							®	—					®	—	
	24-hr ABPM				®	—		®	—					®	—	
	Cognitive Function					•					•				•	
	Blood Vessel Tests					•					•				•	
	MRI (CVR, MRE)					•					•				•	

Abbreviations: PHQ-9, Patient Health Questionnaire 9; MRI, magnetic resonance imaging; PROMIS, patient-reported outcome measurement information system; PSQI, Pittsburgh Sleep Quality Index; APOE, apolipoprotein E; ABPM, ambulatory blood pressure monitoring; CVR, cerebrovascular reactivity; MRE, magnetic resonance elastography; MAQ, modifiable activity questionnaire. **Notation:** • indicates measurement will happen on the specified visit; ® — indicates measurement will happen between specified visits.

6.3 Protocol Schema

This schematic depicts the overall study design and outlines the order of key testing visits and outcome measures. Specific details regarding which tests are performed at each visit are described in the **Schedule of Activities** table on the previous page. If a measurement is not performed on a specific visit, due to equipment failure and/or timing issues, the measurement may be repeated on another visit. More specific details regarding each procedure are included below. The purpose of this study is to gain preliminary data for an R01 proposal aimed at improving brain health through dietary modification of added sugars.

6.4. List of Procedures - The order, frequency and visit(s) at which each measurement will be made is described in the **Schedule of Activities** table above.

Eligibility Measures – The following information will be collected to determine eligibility. Some measures may be repeated at other time points as noted in Table 6.1.

Informed Consent - Subjects will meet with the PI or designated member of the study team to review and sign the informed consent form. Individuals trained to administer the informed consent are listed in Table 3.1. The study team member will walk the subject through the consent form and will answer any questions that the subject may have prior to providing their written consent. As documentation of the informed consent, the subject and the investigator performing the consent will sign (or eSign) the informed consent form and a copy of the signed consent form will be given to the subject.

Subject Demographics – A participant intake form will be used to gather basic information including date of birth, sex, race and ethnicity. An equal number of men and women between the age of 50-64 will be enrolled. Race and ethnicity will be gathered for reporting of basic subject characteristics.

Medical History – Subjects will provide information about any chronic medical conditions that they have been diagnosed with, previous hospitalizations and medical procedures, current prescription and over-the-counter medications or supplements, known allergies, health habits (e.g., smoking and alcohol use), and any current medical conditions or symptoms. Subjects diagnosed with a chronic illness or neurological condition will be excluded.

Gynecological History – Because of the unique age-range of this demographic, we recognize that a small proportion of women may still be pre- or peri-menopausal at the time of screening. Because of the small sample size in this initial pilot study and the influence of reproductive hormones on vascular function^{1,2}, we will only enroll postmenopausal women in this pilot study to reduce potential variability. Female participants will answer questions about their menstrual history to confirm that they are postmenopausal. Menopause status (either surgical or nonsurgical) will be confirmed in all women as a cessation of menses for >1 year; women taking hormone replacement therapy in the preceding year will be excluded from the study³.

Patient Health Questionnaire 9 (PHQ-9) – A brief, 9-item survey will be used to confirm that subjects do not have major depressive disorder, as this can result in cognitive impairment and impact the primary study results. Subjects must score < 10 on the PHQ-9 to be eligible for this study.

MRI Safety Form – Subjects will answer questions about any implanted metal or devices (e.g., a pacemaker) as well as feelings of claustrophobia to determine if they are eligible to undergo MRI scanning. Because the primary outcomes of this study will be obtained using MRI, subjects must qualify for the MRI scan to be enrolled in this study. We will repeat this form before each MRI scan.

COVID-19 Questionnaire - We will ask subjects about their history with COVID-19, including if they were ever hospitalized or experienced severe symptoms, and details regarding vaccination. Subjects that previously had a severe case of COVID-19 will be excluded from this study. To avoid any influence of an acute inflammatory response on our primary outcomes, we will delay baseline testing on subjects who are planning to become vaccinated until 1 week after their final vaccination dose. We will repeat this form on each day that subjects visit the lab to confirm that there are no changes.

Modifiable Activity Questionnaire (MAQ) - Because high levels of physical activity affect vascular function and brain health, we will administer the Modifiable Activity Questionnaire (MAQ) at baseline and exclude subjects who habitually perform an excessive amount of physical activity.

3-Day Diet Record - Participants will be asked to record everything they eat, including portion sizes, over a 3-day period, including two weekdays and 1 weekend day. This log will be returned during their next screening visit. The study nutritionist will analyze the results prior to enrollment. We will only enroll individuals with a habitual added sugar intake between 10-15% of total energy intake to ensure that our study group is reflective of the average American intake based on the National Health and Nutrition Examination Survey (NHANES)⁴.

Height and Body Mass – We will measure body height and mass for reporting of basic subject characteristics and for calculating body mass index (BMI; kg/m²). Subjects with a BMI < 30 kg/m² will be excluded unless their percent body fat is within normal range (see below).

Body Composition – Body composition (% body fat) will be determined using bioelectrical impedance which uses low-level electrical currents through the body to calculate impedance, which is proportional to the amount of body water in adipose tissue. This test will be used primarily as a control variable; however, it may also be used to confirm eligibility based on BMI (as indicated by a % body fat > 25% for men and >33% for women). A tape measure will be used to capture waist circumference.

Vital Signs - Blood pressure and resting heart rate will be measured from the non-dominant arm in the seated and/or supine position after at least 10 minutes of quiet rest using a semi-automated blood pressure device. Repeat measurements will be made (with 2 minutes of quiet rest between recordings) until 3 blood pressure values obtained are within 5 mmHg of one another. These values will be averaged to determine resting systolic and diastolic blood pressure and pulse pressure. Because we are interested in determining the effect of the diets on blood pressure, we will exclude subjects with stage 1 or stage 2 hypertension as defined by a systolic BP \geq 130 mmHg or a diastolic BP \geq 90 mmHg.

Screening Blood - Blood will be drawn by the research nurse or trained member of the research team. Screening blood will be sent to LabCorp for analysis of standard clinical blood chemistry including: a comprehensive metabolic panel, hemoglobin A1C, complete blood count with differential, and a lipid panel which will be used for determination of eligibility and for reporting baseline subject characteristics. With the exception of hemoglobin A1C which is not expected to change over the short duration of this trial, these clinical labs will be repeated at the end of each diet to determine if there are any changes in metabolism (see Table 6.2 for complete description of blood markers measured at each visit).

Control Measures – The following information will not be used to determine eligibility but will serve as important control information.

Family History - A family history questionnaire will be used to obtain information regarding family history of cardiovascular diseases, cancer, diabetes and Alzheimer's disease in order to determine if family history may account for any differences between diets.

Patient Reported Outcomes - Subjects will complete the Patient Reported Outcomes Measurement Information System (PROMIS) 57-item questionnaire to assess self-reported feelings about physical function, anxiety, depression, fatigue, sleep disturbance, social engagement, and pain intensity.

Sleep Questionnaires - Self-reported sleep quality will be assessed using the Pittsburgh Sleep Quality Index (PSQI) and the 17-item Munich Chronotype Questionnaire (MCQ). The PSQI is a 19-item self-report tool that assesses healthy sleep metrics over a 1-month time interval. The 17-item MCQ determines sleep midpoint for work and free days in the last month.

Sleep Quality - Participants will be provided with an Actiwatch accelerometer watch (Phillips) for an objective assessment of sleep quality. Subjects will be asked to wear the device on their non-dominant wrist for ten days and return it at their next visit.

Physical Activity Questionnaire – Subjects will complete a questionnaire using the International Physical Activity Questionnaire (IPAQ) to determine physical activity measures. The 27 questions of the IPAQ inquiries about physical activity in the last 7 days across 5 domains that relate to occupation, transportation, housework, recreational activity, and time spent sitting,

Food Preference Questionnaire – Subjects will complete a brief questionnaire to determine their food preferences. This information will be used by the nutritionist to design specific diets that are catered to each subject's food preferences to improve compliance and to determine their energy needs.

APOE Genotype – Blood will be sent to LabCorp for determination APOE genotype using a standard clinical PCR test (LabCorp; CPT: 814401).

Blood Biomarkers - Additional blood will be retained by the Neurovascular Aging Laboratory for isolation of serum, plasma and peripheral blood mononuclear cells (PBMCs) which will be used for assessing markers of oxidative stress, inflammation, mitochondrial function, and additional blood lipid factors.

Urine Collection – Urine will be collected for determination of uric acid, which will be used as a marker of adherence to each diet. Urine uric acid is expected to increase during the high sugar diet but not during the low sugar diet.

Home Body Weight and Appetite – Subjects will be provided with an electronic scale and will be asked to record their body mass daily, using an electronic (REDCap) survey that will be emailed to them at the same time each day to confirm that they are consuming the isocaloric diet and not gaining or losing body mass. They will also be asked to rate their perceptions of hunger and satiety using a visual analog scale (0-100 mm).

24-hour Urine Collection – Subjects will collect all of their urine for 24 hours to measure urine sodium concentration as a measure of compliance to each diet.

Outcome Measures – The following measures will be made for testing primary and secondary hypotheses. All measures will be made on the same day (e.g. baseline or day 10 of each diet) with a short break in between arterial stiffness testing to drive to the MRI center.

Visits 2.1, 3.2 and 4.2 (Location: Center for Biomedical and Brain Imaging)

MRI Scan – The MRI scan will include the following tests:

- Cerebrovascular Reactivity (CVR) will be measured as the maximal change (from rest) in total cerebral perfusion during 3-minutes of hypercapnia (+9 mmHg increase in $P_{ET}CO_2$) using pseudo-continuous arterial spin labeling (PC-ASL)⁶, which uses radio-frequency pulses to magnetically label the water in the blood as an endogenous tracer ⁶ and thus can be performed without the need for a contrast agent. Hypercapnia will be induced using an MR-compatible prospective end-tidal targeting system which allows for precise and repeatable manipulation of $P_{ET}CO_2$ on a breath-by-breath basis through a face mask using a computerized gas blender (RespirActTM)⁷⁻⁹. Beat-to-beat BP will be assessed using an MRI-compatible non-invasive BP (NIBP) monitor (Biopac, Goleta, CA) to normalize blood flow to mean arterial blood pressure.
- Brain Microstructural Integrity will be assessed by Magnetic Resonance Elastography (MRE) of the brain. During the acquisition of MRE images, the subject's head will be vibrated using the Resoundant Acoustic Driver System. The Resoundant is an FDA-approved device for inducing small vibrations in a scan subject. The device consists of a small, pillow-like pad that is attached in the MRI head coil and that the subject's head rests on. This pad receives vibrations from tubing that attaches to an active driver placed in the control room. The vibrations received result in a small up-down vibration of the subject's head. The active driver is activated in concert with the MR scanner and is controlled by the investigator performing the scan.

Structural T_1 - and T_2 -weighted and BOLD MRI images will be acquired following MRE and ASL acquisitions, which are necessary for comparing MRE and ASL findings with brain structure and activity. There will be no vibration during these additional scans. During all scans the subjects will wear disposable earplugs and/or headphones to reduce scanner noise. Participants may also be asked to wear a pulse oximeter on their finger to measure heart rate or a respiratory belt around their chest to measure breathing. This is to observe any potential MRE signal changes from movement associated with breathing or heart rate. Both devices are provided by Siemens with the MRI scanner, are MR-safe and MR-compatible, and interface with the MRI scanner software.

Visits 2.2, 3.3 and 4.3 (Location: Neurovascular Aging Laboratory)

24-Hour Ambulatory Blood Pressure (ABPM) – Subjects will be asked to wear a blood pressure monitor on their upper arm for 24 hours at baseline and during the final day of each diet. The blood pressure cuff will be set to automatically take their blood pressure every 20 minutes during the day and every 30 minutes at night. If possible, subjects will be instructed to sit down and relax when they feel the upper arm blood pressure start to inflate. They will also be asked to refrain from caffeine, alcohol, and exercise on this day.

Arterial Stiffness – The following measures will be made to characterize arterial stiffness.

- Pulse Wave Velocity (PWV) – We will use transcutaneous tonometry to measure the pulse in the carotid artery while placing a standard blood pressure cuff around the thigh to measure the pulse in the femoral artery. The pressure wave at each recording site will be aligned to the cardiac cycle

using a 3-lead ECG and PWV will be calculated as the distance between measurement sites divided by the transit time of the arterial pulse wave.

- Pulse Wave Analysis – We will derive central (aortic) pulse pressure (PP), augmentation pressure (AP) and augmentation index (AI) from the radial artery pulse wave using applanation tonometry.
- Carotid artery compliance – We will record a high-resolution ultrasound video of the carotid artery and use applanation tonometry to determine carotid artery pulse pressure. Compliance will be calculated as the change in carotid diameter for a given change in pressure.

Brain Blood Vessel Test - A small ultrasound probe will be placed on the top of the skin above the temple, and we will record how fast the blood is moving through a major artery in the brain. At the same time, we will measure the amount of carbon dioxide (CO₂) in the air that is exhaled by having a soft flexible tube in the front of the nose with ~1 cm extensions that are inserted into the tips of the nostrils and respiration will be measured using a flexible respiration strap. This brain blood vessel test will be measured in response to an acute (~30 second) breath hold, as previously described⁵. The participant will be monitored for signs of distress and the test will be stopped immediately if they express discomfort. The breath-hold test is self-guided and the participant is free to breathe at any time.

Cognitive Function – Memory function will be assessed by performance on the Hopkins Verbal Learning Test (HVLT-R), The Brief Visuospatial Memory Test (BVMT-R), and the NIH Toolbox Pattern Comparison and Flanker tests. The HVLT-T and BVMT-R have multiple versions to prevent learning tests. We will choose three versions of this test at the beginning of the trial and will administer a different version at each visit. The order will be counterbalanced to avoid any effect of test version on cognitive outcomes. The selected NIH Toolbox texts are less prone to learning effects.

Study Restrictions

Subjects must avoid over-the-counter medications for 48 hours, vigorous aerobic exercise or alcohol for 24 hours, and all food, supplements and caffeine for ≥ 12 hours before testing visit but will be allowed to consume water. There are no restrictions for Visit 1.1, unless this visit is combined with Visit 1.2, in which case the above restrictions apply.

Table 6.2. Table of Blood Tests

	Test #	Type	Volume	Visit 1.2	Visit 3.3	Visit 4.3
Screening Labs						
Comprehensive Metabolic Panel	322000	SST Serum	4 mL	X	X	X
Complete Blood Count	005009	EDTA Plasma	4 mL	X	X	X
Lipid Panel	303756	SST Serum	4 mL	X	X	X
Control Measures						
Hemoglobin A1C	001453	EDTA Plasma	4 mL	X	---	---
APOE genotype	504040	EDTA Plasma	4 mL	X	---	---
Blood Biomarkers						
Oxidative Stress/Inflammation	---	EDTA Plasma	4 mL	X	X	X

	---	SST Serum	4 mL	X	X	X				
PBMC's	---	EDTA Plasma	32 mL	X	X	X				
		Total Per Visit		60 mL (4TBL)	52 mL (3.5 TBL)	52 mL (3.5 TBL)				
				Total Volume for Study (mL)		164 mL (11 TBL)				
						Total Volume for Study (pints)				
						1/3 pint				

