7. STUDY POPULATION AND RECRUITMENT

Study Population – The target enrollment for this study is 200 healthy adult men and women between 50-64 years of age, with a target completion of 40 participants. This age group has been defined by NIH as being at high risk of accumulating cardiometabolic risk factors that preclude chronic age-related diseases¹⁵⁻¹⁷. To avoid any influence of baseline diet (e.g., chronic consumption of a high-sugar diet prior to enrollment), will only enroll those with a habitual intake of added sugar that is reflective of the average American intake (~13% of total calories) based on the National Health and Nutrition Examination Survey (NHANES)¹⁸. This will increase the likelihood of observing changes in our primary outcome variables in response to the proposed research diets which are designed to deviate from baseline proportion of added sugars by about 10% of calories in each direction. Importantly, even if

subjects are close to the upper or lower cutoff, we are still likely to observe changes in primary outcomes when placed on the opposite arm of the crossover. Because this is a pilot study, we will analyze the data after the first 5-10 participants have completed the trial and ensure that we are seeing an effect of the diets on the primary outcome variables. If we do not see an effect, we will amend the protocol to increase the duration and/or modify the composition of the diets.

To be eligible to participate, volunteers must meet the following specific enrollment criteria:

Inclusion Criteria:

- ability to provide informed consent;
- men and postmenopausal women aged 50-64 years;
- habitual intake of added sugars ≤15% of total calories¹⁸;
- systolic BP < 130 mmHg; diastolic BP < 90 mmHg¹⁹;
- body mass index (BMI) <30 kg/m² and % body fat < 25% for men and < 33% for women
- fasting triglycerides < 200 mg/dl (< 2.3 mmol/L)²⁰;
- LDL cholesterol <160 mg/dl (4.14 mmol/L)²¹
- fasting plasma glucose <126 mg/dl (<7.0 mmol/L) and hemoglobin A1C < 6.5% at screening²²;
- weight stable in the prior 6 months (≤ 2 kg weight change);
- blood chemistries indicative of normal liver enzymes and renal function (estimated glomerular filtration rate using the MDRD prediction equation must be >60 ml/min/1.73 m²)

Exclusion Criteria:

- current use of medications or supplements known to lower blood triglycerides or cholesterol (e.g., fibrates, statins, high dose niacin, high dose omega-3 supplement);

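### More than a year without menses cannot confirm menopause when bleeding stopped because of uterine surgery or ablation with the ovaries retained, so the menopause criterion is weaker than its stated purpose needs (minor)

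*Protocol*

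**What the plan says.** The Gynecological History entry in Protocol section 6.4 gives the reason for the criterion and the test for it. The reason is the small sample together with "the influence of reproductive hormones on vascular function"; hence "we will only enroll postmenopausal women in this pilot study to reduce potential variability". The same entry accepts that, in this age range, "a small proportion of women may still be pre- or peri-menopausal at the time of screening".

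The test comes from self-report ("Female participants will answer questions about their menstrual history to confirm that they are postmenopausal") and is the same for every route to menopause: "Menopause status (either surgical or nonsurgical) will be confirmed in all women as a cessation of menses for >1 year". A further condition concerns hormones taken as treatment: "women taking hormone replacement therapy in the preceding year will be excluded from the study".

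The inclusion list in Protocol section 7 reads "men and postmenopausal women aged 50-64 years" and does not define the term. The one-year hormone-therapy exclusion appears in neither the inclusion nor the exclusion list there.

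**The concern.** The criterion is aimed at ovarian hormone status, but the test measures bleeding. The two usually go together. They separate when the uterus has been removed or its lining ablated and the ovaries remain: menses end while ovarian hormone production may continue. By naming surgical cases and giving them the same test as everyone else, the protocol brings in the group for whom that test says least.

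At stake is precision in the Aim 1 primary outcomes named in the SAP (24-hour systolic pressure, arterial compliance and cerebrovascular reactivity). These belong to the vascular domain that the criterion is meant to protect. The description of the enrolled women as postmenopausal would also be less exact than it appears.

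**Working it through.** The plan states no figure to reproduce. The check is to apply the rule as written and then look for any other provision that would catch the cases it misses.

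**Step 1. Apply the rule to each kind of woman aged 50-64 who takes no hormone therapy.**

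- Still menstruating: fails the test, as intended.
- Natural cessation for more than a year, with nothing suppressing bleeding: passes, as intended.
- Both ovaries removed more than a year ago: passes, as intended.
- Hysterectomy or ablation more than a year ago that ended menses, ovaries retained: passes whatever her ovarian function. If she is still pre- or peri-menopausal, she is the woman the criterion was written to keep out.

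**Step 2. Look for another safeguard.**

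- Protocol section 7 requires postmenopausal status but gives no definition, and nothing in its exclusion list concerns ovarian status.
- Screening bloods are "a comprehensive metabolic panel, hemoglobin A1C, complete blood count with differential, and a lipid panel". Table 6.2 adds APOE genotype, markers of oxidative stress and inflammation, and mononuclear cells. No reproductive hormone is listed.
- The Medical History entry in section 6.4 records past procedures, so a hysterectomy should come to light at Visit 1.1. No rule says what to do with that answer when judging menopausal status.
- The hormone-therapy exclusion covers hormones taken as treatment, not the woman's own ovarian function.

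None of these closes the gap.

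**Step 3. Trace the consequence through the design.**

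Each woman is measured at baseline and on day 10 of each diet. The two day-10 tests are separated by the washout plus the second diet period: 14 + 10 = 24 days. A crossover removes what is stable within a person, but not hormone levels that differ between visits. In a woman who is still cycling or in transition, that variation enters the within-person error. Covarying for sex, as the SAP plans, cannot remove it, because sex does not change between visits.

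Diet order is randomized, so hormone state at a visit has no systematic link to the diet eaten. The expected result is noise, not bias, in the diet contrast.

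**Step 4. Can the size be computed?**

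The protocol plans equal numbers of men and women, so about 40 / 2 = 20 women at the protocol's completion target, or 30 / 2 = 15 at the sample size on which the SAP bases power. If a fraction f of all completers carried extra within-person variance equal to r times the ordinary amount, average error variance would rise by the factor 1 + f × r. To find f one would need the share of recruited women with uterine surgery or ablation and retained ovaries, and the share of those not yet past menopause. To find r one would need the hormone-related variance of each outcome. The documents supply none of these, so no figure is given.

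**The case against.** The strongest reply is that surgical menopause ordinarily means removal of the ovaries. On that reading the one-year condition is a duration requirement added to a status already established, and a screener who knew that the ovaries were intact could refuse the woman under the section 7 criterion alone. This may well be the intention. But the protocol does not say it, and the one test that it sets for confirming status cannot tell the two surgical histories apart.

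A second reply is that the Menstrual History Form, listed under Supporting Documentation in Protocol section 15 but not reproduced, may already ask about type of surgery. That is possible, and it would be wrong to assert that the question is missing. What can be said is that no written eligibility rule acts on the answer.

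A third reply stands in full. The stated aim is to reduce variability, not to abolish it. The rule still keeps out every menstruating woman and recent users of hormone therapy. The protocol expects only a small share of women in this age range not to have reached menopause, and those who also had uterine surgery or ablation with ovaries kept are a subset of that share.

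A reader might also infer three stronger things that the documents do not support:

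- *That the diet comparison is biased.* Randomized order and within-person contrasts argue against this.
- *That comparisons of women with men are distorted.* The SAP plans no such comparison; sex is a blocking factor and a covariate only.
- *That women on recent hormone therapy can be enrolled because section 7 omits the exclusion.* The exclusion is operative where it stands, among the eligibility measures in section 6.4. Its absence from section 7 is an inconsistency of presentation.

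**Conclusion.** The point holds as a minor one. The menopause rule, as written, cannot identify menopausal status in women whose menses stopped through hysterectomy or ablation with ovaries retained, and nothing else in the protocol does so. A few women who are still pre- or peri-menopausal, probably at the younger end of the range, could therefore be enrolled.

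It goes too far to say that the criterion is defeated. That is true only of the individual woman who slips through; across the trial the criterion is weakened. It also goes too far to attach a probability of enrolling at least one such woman. Any figure would rest on an assumed rate of retained-ovary surgery, and would count women of unknown ovarian status, not women who are still cycling.

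The conclusion rests on two things: the literal wording of the test, and the general fact that loss of the uterus or its lining ends menses without necessarily ending ovarian hormone production. The extra noise falls on the Aim 1 vascular outcomes in an unknown, probably small, number of women.

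**What to change.** State the rule by route in the Gynecological History entry of Protocol section 6.4:

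- Nonsurgical: more than a year without menses, not explained by uterine surgery, ablation or a device that suppresses bleeding.
- Surgical: removal of both ovaries.
- Women whose menses stopped for another surgical or device reason, with ovaries in place, do not qualify on absence of menses alone.

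Apply it from the medical and menstrual histories already taken at Visit 1.1, checking that the menstrual form records type of surgery, whether the ovaries were kept, and any ablation or device. Repeat this rule and the one-year hormone-therapy exclusion in the section 7 lists, so that the two sections agree.

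The cost is a protocol wording change, possibly a small edit to the form, and a few more screen failures, some of them women who are truly postmenopausal but cannot show it by this route. Section 7 plans to enrol 200 to obtain 40 completers, which leaves room for that loss.
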